6. STATISTICAL CONSIDERATIONS

6.1. Summary Statement

Patients will be in one of 2 cohorts, those receiving 1) curative intent surgical resection of primary rectal cancer or 2) radiation therapy without surgical resection for treatment of

pelvic cancer, other than of the rectum. For the patients who have had surgical resection, preliminary safety and efficacy data exist so this will be an efficacy trial confirming the preliminary data. For patients who were treated with XRT only, this is a preliminary trial to establish safety and provide a first estimate of efficacy. In this initial study, stratification based on type of radiation, method and/or dose will only be conducted in a hypothesis generating manner to explore future trial options if battery implantation rates are extremely low in cohort 2. While the methods will be carried out the same, the level of evidence for conclusions at the end of the trial will be different for each.

6.2. Analysis Subgroups

All patients who sign consent and take the visit 1 questionnaires, and do not have insurance denial as the reason for no SNS placement, will be considered evaluable for this study. Patients who return for their SNS placement appointment will be included in analyses of the endpoints.

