5. STUDY METHODS

Patient Selection

Both study cohorts will be evaluated and managed at the same. Total accrual to this study is 66 patients for enrollment of 60 evaluable patients to the study, 30 patients into each cohort, at the UT MD Anderson Cancer Center (UTMDACC) in Sugar Land, Texas. Patients meeting study eligibility will be screened prospectively in relevant UTMDACC clinics, which are a likely source of patients to be identified for screening, or through physician referral to the study.

Study Enrollment

All patients will undergo a complete history and physical, per routine standard of care. Patients disclosing FI or LARS will sign consent and be pre-registered on the study in CORe for screening and will complete questionnaires (on paper, over the phone/teleconference system, or electronically through REDCap) related to general quality of life, FI severity, and LARS.

Patients may access the questionnaires electronically in the REDCap system via a link sent to them by email or MyChart (Appendix K). Patients will then undergo an anorectal manometry for pelvic pressure readings per standard of care. Then, patients who disclose appropriate bowel dysfunction (urgency, alternating diarrhea and constipation, fragmentation, obstructive defecation, and stacking) and with abnormal anorectal manometry readings and questionnaire responses indicating study eligibility, will proceed with enrollment in the study. Patients who are found not to meet eligibility based on bowel dysfunction reporting, questionnaire responses and anorectal manometry results will be removed from the study. Patients meeting all eligibility criteria with insurance pre-authorization for all procedures will be enrolled on the study.

Patients on-study with lab results described below before SNS placement will be given 30 days to improve and will be re-evaluated. Patients will have these tests ordered for routine standard of care based on the determination of the physician. If no improvement at 30 days, patients will be taken off study, data collected up to this point may be used in study reporting.

- ANC <1.7, INR >1.3, platelet count <50K

On-study patients requiring systemic therapy for an infection before SNS placement will be given 30 days to improve and will be re-evaluated. If no improvement at 30 days, patients will be taken off study, data collected up to this point may be used in study reporting.

Procedure to Obtain Informed Consent

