8. International Consultation on Incontinence Questionnaire-Female Lower Urinary Tract Symptoms (ICIS-FLUTS) if female and International Continence Society Male Short Form (ICSmaleSF) if male: Validated instruments to measure urinary dysfunction.
9. Low Anterior Resection Syndrome (LARS) Bowel Function Questionnaire: This is a validated instrument, to be provided only to the restorative surgery cohort, designed to assess clinical severity of symptoms of LARS outside of just FI and will be a significant tool to address extending criteria for SNS use outside of FI.
10. EORTC QLQ-CR29: this is a quality of life instrument validated for patients with colorectal cancer. This will be provided to all patients.

Study Visits

Initial Evaluation/Visit 1: Patients are referred to the clinic for reported refractory FI or LARS. Upon arrival to their initial clinic visit, the patients will complete the validated questionnaires and instruments (on paper, over the phone/teleconference system, or electronically through REDCap), as well as an ARM. A minimum score from the FISI will not be required as this was not required for the initial studies in the benign disease patients, though it is anticipated that their scores will be around a score of 30, a number defined as what is typical for patients who have a significant quality of life impairment due to their reported fecal incontinence. The results will then be reviewed for appropriateness to be considered eligible for the study. Patients will sign consent and then be enrolled after appropriate evaluation by the clinical and research teams and all inclusion and exclusion criteria are met. The remaining questionnaires will be completed and a complete review of symptoms and physical exam will be performed per standard of care. A post-void residual bladder scan will be performed at this visit after enrollment as well. After all objective data are collected, each patient will be scheduled for surgery for placement of a sacral nerve stimulator under general anesthesia in the operating room as per standard of care. All patients are asked to begin recording all daily bowel and bladder habits in the bowel and bladder

trackers to serve as their baseline function. Necessary preoperative testing will be ordered and completed at UTMDACC including appropriate consultant visits as per standard of care for any operation.

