6.3. Endpoints

Primary Endpoints

The primary endpoint is SNS Success. *SNS Success* will be measured as a patient having the battery implanted at visit 3 which can only happen if they've achieved improvement in fecal incontinence at visit 3. Patients who do not have the SNS placed, for any reason other than insurance coverage issues, will count as not having a success.

Fecal incontinence will be measured by the physician as the total number of gas, mucus, liquid stool, and solid stool accidental leakage events reported in the bowel diaries.

Improvement will be determined by the physician based on bowel diary comparisons recorded before SNS lead placement at visit 1 to after lead placement at visit 2. This is done at visit 3 when the patient presents for consideration of placement of the implantable battery. Any patient who comes in for SNS placement but the SNS cannot be successfully placed for any reason other than insurance reasons will count as not having improvement. Patients meeting this improvement will have their *battery implanted*. Patients will be counted as having their battery implanted if it is implanted at Visit 3 if they had the SNS placed at Visit 2.

Secondary Endpoints

- **FISI** overall questionnaire summary
- **FIQOL** overall questionnaire summary
- **ARM** score
- **EQ-5D-5L**
- **ICSmaleSF** or **ICIS-FLUTS** (females)
- **MSKCC BFQ (for restorative surgery cohort)**
- **LARS Score Bowel Function Questionnaire (for restorative surgery cohort)**

- **CCIS (for radiation only cohort)**
- **Bowel Diaries**
- **Bladder Diaries**
- **EORTC QLQ-CR29**
- **FISI, FIQOL, EQ-5D-5L, ICSmaleSF or ICIS-FLUTS, MSKCC, EORTC QLQ-CR29 and CCIS will also be collected at 1 and 3 years for long-term evaluation.**

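### The denominator for SNS Success is contradictory: one line of text counts patients who fail manometry screening as non-successes, another leaves them out

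*Combined protocol and SAP*

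**What the plan says.** **Text that brings screen failures in.**

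- Section 6.2, first sentence, treats as evaluable "All patients who sign consent and take the visit 1 questionnaires, and do not have insurance denial as the reason for no SNS placement". Eligibility, manometry and enrolment are not mentioned.
- Section 5, Study Enrollment, gives the order: "Patients disclosing FI or LARS will sign consent and be pre-registered on the study in CORe for screening and will complete questionnaires". Manometry comes next: "Patients will then undergo an anorectal manometry for pelvic pressure readings per standard of care".
- Section 6.3: "Patients who do not have the SNS placed, for any reason other than insurance coverage issues, will count as not having a success".

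**Text that keeps them out.**

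- Section 6.2, second sentence: "Patients who return for their SNS placement appointment will be included in analyses of the endpoints". Surgery is scheduled only after enrolment, so a patient who fails screening has no such appointment.
- Section 5, Study Enrollment: "Patients who are found not to meet eligibility based on bowel dysfunction reporting, questionnaire responses and anorectal manometry results will be removed from the study".
- Section 5, Visit 1, puts questionnaires and manometry first and consent afterwards: "Patients will sign consent and then be enrolled after appropriate evaluation by the clinical and research teams and all inclusion and exclusion criteria are met".
- Section 6.3 also has a narrower rule, limited to "Any patient who comes in for SNS placement but the SNS cannot be successfully placed for any reason other than insurance reasons".
- Section 6.5, safety table, counts as evaluable only patients with a cohort-limiting event (CLE), a battery implant, or leads removed for failure.

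No section says whether a patient removed at screening counts toward the 30 per cohort or toward the looks after every 6 patients.

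**The concern.** SNS Success ought to estimate the response rate among eligible patients offered the device. Under the first set of statements, a patient who consents, answers the questionnaires and then misses either manometry limit (resting tone below 40 mmHg and maximal tolerance below 200 mL are both required) is evaluable and a non-success without ever being a candidate for stimulation. The reported rate would then mix device response with the screen-failure rate.

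The same denominator drives the primary estimate, the futility looks in 6.5 and the 50% criterion in 6.6. The trial is single-arm, so there is no control group in which the same dilution would occur. If the reading is chosen after data have been seen, that choice could change a stop-or-continue decision.

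**Working it through.** **1. Reproducing the plan's figures.**

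- Precision (6.4): 15/30 with a beta(1,1) prior gives Beta(16,16). Its 5th and 95th percentiles are 35.66% and 64.34%; the plan states 35.7% and 64.3%.
- Futility boundary (6.5): the largest s with P(Beta(1+s, 1+n−s) < 0.5) > 0.95. For n = 6, 12, 18, 24, 30 this gives 0, 3, 5, 7, 10, as stated.
- Safety boundary (6.5): the smallest x with P(Beta(0.6+x, 1.4+n−x) > 0.3) > 0.95. This gives 5, 7, 9, 12, 14, as stated.
- Operating characteristics, by exact enumeration with response and CLE independent and a CLE rate of 0.1: at success 0.40, early stop 0.327 and mean 24.6 patients (stated 0.33, 24.6); at 0.50, 0.101 and 28.3 (stated 0.10, 28.3); at 0.70, 0.0025 (stated 0.003).

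The boundaries are correct. What is unclear is the population to which they apply.

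**2. If screen failures are counted as non-successes.**

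Let p be the true success rate among eligible patients and f the share of the evaluable set who failed screening. The scored rate is p(1−f). The documents give no value for f, so 0–40% is an assumption.

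The plan's own table shows the effect for p = 0.50. At f = 20% the scored rate is 0.50 × 0.80 = 0.40, and at CLE rate 0.1 the stated early-stop probability goes from 0.10 to 0.33. At f = 40% the rate is 0.30 and the stated value is 0.68.

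For other values of p, an exact calculation used the futility looks 0/6, 3/12, 5/18 and 7/24, ignoring CLE stops:

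| p | f | Scored rate | Early futility stop | At least 15/30 |
|---|---|---|---|---|
| 0.60 | 0 | 0.60 | 0.020 | 0.896 |
| 0.60 | 20% | 0.48 | 0.132 | 0.476 |
| 0.70 | 0 | 0.70 | 0.002 | 0.992 |
| 0.70 | 10% | 0.63 | 0.011 | 0.945 |
| 0.70 | 20% | 0.56 | 0.041 | 0.793 |
| 0.70 | 30% | 0.49 | 0.116 | 0.520 |
| 0.70 | 40% | 0.42 | 0.268 | 0.235 |
| 0.791 | 10% | 0.712 | 0.002 | 0.99 |
| 0.791 | 20% | 0.633 | 0.011 | 0.95 |
| 0.791 | 30% | 0.554 | 0.045 | 0.77 |
| 0.791 | 40% | 0.475 | 0.142 | 0.45 |

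The value 0.791 is the permanent implantation rate that Section 2 cites from a systematic review; it serves here only as a scenario. Another way to see the effect: with 6 screen failures among 30, the other 24 would need 15/24 = 62.5% success to reach 15/30.

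**3. If screen failures are left out of the endpoint but fill evaluable places.**

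Take 6 of the 30 places so used, 24 analysed and 12 successes. Beta(13,13) gives a 90% interval of 34.1–65.9%, against 35.7–64.3% with 30 analysed. The estimate is less precise but not biased, provided the looks also count only analysed patients.

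**The case against.** A reader might infer that the plan has decided to score every screen failure as a device failure, so that its success rate is certain to be biased downward. The documents do not support that.

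- The second sentence of 6.2, taken alone, removes these patients from the endpoint.
- Section 5 separates pre-registration from enrolment, removes ineligible patients, and describes the 60 evaluable patients as enrolled. It allows data to be used for on-study patients later taken off for laboratory values or infection, and gives no such rule for patients removed at screening.
- It is not certain that a screen failure has taken the Visit 1 questionnaires in the sense of 6.2. Study Enrollment lists only quality of life, incontinence severity and LARS before manometry, and the Visit 1 text leaves the remaining instruments until after enrolment.
- Section 6.4 says insurance cases are not evaluable. It does not say that insurance is the only reason.
- The large effects need a share of 30–40%, for which the documents offer no basis. At 79.1% true success, shares of 10% and 20% do little harm.

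All of this stands, and it shows that the exclusion reading is reasonable. It does not make that reading the stated rule. Evaluable cannot simply be equated with enrolled: Study Enrollment enrols only patients with insurance pre-authorization, yet 6.2 and 6.4 still have to take insurance denials out of the evaluable set, which suggests a set that begins at consent. Removal from the study does not settle it either, since patients whose device is removed at Visit 3 also end participation and are still analysed. The second sentence of 6.2 also conflicts with the broad non-placement rule in 6.3. The Visit 1 consent order avoids the problem only by contradicting Study Enrollment.

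**Conclusion.** The primary-endpoint denominator is contradictory and should be settled before any interim look. The text supports both counting patients who fail manometry screening as non-successes and excluding them.

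The size of the consequence depends on the reading and on a screen-failure share that the documents do not give. If they are counted, at 70% true success among eligible patients and shares of 10–40%, the early futility stop rises from 0.002 to 0.011–0.268 and the chance of at least 15/30 falls from 0.992 to 0.945–0.235. The effect is small when true success is high and few fail screening. If they are excluded from the endpoint but occupy places, the cost is some precision and no bias. These figures are conditional scenarios and do not predict what the trial will report.

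**What to change.** Use one primary analysis set throughout 6.2–6.6: consented, all eligibility criteria confirmed including manometry, enrolled after pre-registration, and placement not prevented by insurance denial.

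- Count non-placement after enrolment, for any other reason, as not a success.
- Delete the second sentence of 6.2, or align it with 6.3. Rewording the evaluable definition alone would leave two denominators.
- Report patients removed at screening separately, and keep them out of the 30 per cohort, the looks every 6 patients and the SNS Success denominator.
- Reconcile the order of consent and screening in the Study Enrollment and Visit 1 texts.

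This is a change of wording; the boundaries and operating characteristics need no recalculation. The cost is that more patients may need to be screened to reach 30 per cohort. The accrual ceiling allows only 66 − 60 = 6 spare patients, so the text should also say whether patients removed at screening count toward the 66.

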6.3. Endpoints

Primary Endpoints

The primary endpoint is SNS Success. *SNS Success* will be measured as a patient having the battery implanted at visit 3 which can only happen if they've achieved improvement in fecal incontinence at visit 3. Patients who do not have the SNS placed, for any reason other than insurance coverage issues, will count as not having a success.

Fecal incontinence will be measured by the physician as the total number of gas, mucus, liquid stool, and solid stool accidental leakage events reported in the bowel diaries.

Improvement will be determined by the physician based on bowel diary comparisons recorded before SNS lead placement at visit 1 to after lead placement at visit 2. This is done at visit 3 when the patient presents for consideration of placement of the implantable battery. Any patient who comes in for SNS placement but the SNS cannot be successfully placed for any reason other than insurance reasons will count as not having improvement. Patients meeting this improvement will have their *battery implanted*. Patients will be counted as having their battery implanted if it is implanted at Visit 3 if they had the SNS placed at Visit 2.

Secondary Endpoints

- **FISI** overall questionnaire summary
- **FIQOL** overall questionnaire summary
- **ARM** score
- **EQ-5D-5L**
- **ICSmaleSF** or **ICIS-FLUTS** (females)
- **MSKCC BFQ (for restorative surgery cohort)**
- **LARS Score Bowel Function Questionnaire (for restorative surgery cohort)**

- **CCIS (for radiation only cohort)**
- **Bowel Diaries**
- **Bladder Diaries**
- **EORTC QLQ-CR29**
- **FISI, FIQOL, EQ-5D-5L, ICSmaleSF or ICIS-FLUTS, MSKCC, EORTC QLQ-CR29 and CCIS will also be collected at 1 and 3 years for long-term evaluation.**

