The investigator must obtain documentation of consent from each potential subject prior to participating in a clinical trial.

[figure not shown]
The protocol and informed consent documentation for this study must conform to institutional regulations and local and national laws and regulations. As soon as a potential subject is considered for this study and prior to any other study procedures, each prospective subject will be given a full explanation of the purpose of the study, the procedures to be carried out and the potential hazards. Once this essential information is provided to the subject and once the Investigator believes that the subject understands the implications of participating in the study, the subjects will be asked to provide written informed consent and authorization to access medical records needed for study documentation. Subjects will be required to read, sign, and date a properly executed written Informed Consent Form prior to enrollment and will be assured that they may withdraw from the study at any time without jeopardizing their medical care. They will be given a copy of their Informed Consent Form.

Patients will either be consented in person, or contacted via phone, or through an Institutionally-approved teleconferencing system (i.e., Zoom) and will complete the consent process through Institutionally-approved remote-consenting procedures.

Study Procedures

After study enrollment, patients will undergo scheduled, elective surgery for placement of the sacral nerve stimulator. The initial surgical placement is performed using fluoroscopy-guidance to place a single electrode through the sacral foramen of nerve root 3 via passage through a needle. The SNS device is self-anchoring and device migration is extremely rare; however, this can be surgically corrected. Stimulator migration rarely affects the device function although it impairs patient quality of life.[26] This technique has been previously described.[10] The electrode is then tunneled under the skin in the soft tissue of the buttocks and out the skin toward the hip where it is then connected to an external battery pack and covered, maintained in a sterile dressing and adjusted over the next 2 weeks by the patient. A bowel and bladder habit diary is maintained by the patients for the interval 2 week period.

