After 2 weeks, the patients return to the OR for either removal of the leads if the stimulator did not work, or implantation of a subcutaneous titanium battery with internalization of the electrode as per standard of care. Prior to lead extraction in patients who do not meet criteria for battery implantation, lead position will be re-investigated for appropriate positioning, and if incorrectly positioned due to migration, lead repositioning will be performed and the two week trial period restarted. The patients are discharged home from this outpatient surgery and will complete the bowel and bladder habit diaries. The patients will be required to return to the office at 1 month following their surgery to perform a wound check, symptom evaluation, and again complete study questionnaires (on paper, over the phone/teleconference system, or electronically through REDCap) for comparison, and undergo repeat anorectal manometry and a post-void residual bladder scan.

Validated Questionnaires/Instruments:

1. Fecal Incontinence Quality of Life (FIQoL): this is a quality of life instrument validated for patients with fecal incontinence. This will be provided to all patients.
2. Fecal Incontinence Severity Index (FISI): this is a scoring system validated to objectively quantify fecal incontinence severity. This will be provided to all patients.

3. EQ-5D-5L: This is a general quality of life instrument that is currently used in the GI surgery clinics as part of the prospective rectal cancer study that collects longitudinal quality of life and function outcomes. This will be provided to all patients.
4. Memorial Sloan Kettering Cancer Center Bowel Function Instrument (MSKCC BFI): This is a validated instrument for resected rectal cancer patients designed to assess bowel dysfunction including LARS. This will be provided to patients in the restorative surgery cohort only.
5. Cleveland Clinic Incontinence Score (CCIS): This is a validated instrument for FI specifically in patients whose rectums have not been surgically removed. This will be provided to the radiation only cohort patients.
6. Bowel Diary: Validated bowel diary provided by the device company used to collect daily bowel function.
7. Bladder Diary: Validated urinary diary provided by the device company used to collect daily urinary function.

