Visit 2 (Sacral Nerve Stimulator Lead Placement): Surgery for stage 1 sacral nerve stimulator placement will occur within 30 days after enrollment in the study. The patient will arrive at the pre-operative holding areas at UTMDACC's main campus for their outpatient surgery. The representative for the implantable SNS company (Medtronic) will be present at the operation for assistance with placement of the leads per standard of care and for assistance with patient education following lead placement. The patients are sent home with a diary to record daily bowel and bladder habits during the interval period.

Visit 3 (Assessment of Symptoms and Battery Implantation or Lead Removal): Surgery for stage 2 sacral nerve stimulator battery implantation or lead removal will occur around 2 weeks (+7 days) after SNS placement. The patient will arrive to the holding area with their post-implantation bowel and bladder habit diary from visit 2. Review of the bowel diary information and a review of symptoms from visit 1 and visit 2 with the patient will be completed and then a decision made to either implant the battery or remove the stimulator leads as per standard of care. If the bowel diary reveals $\geq 50\%$ decrease in FI or LARS symptoms between visit 1 and visit 2, the external temporary battery will be replaced with an implantable battery. If the bowel diary reveals $< 50\%$ decrease in FI or LARS symptoms, the previously placed leads and external battery will be evaluated for proper positioning and functioning in the OR and removed if they remain properly positioned. Following the procedure, the patient is discharged home. If the device is removed, their participation in the study is complete, but data collected to this point will still be used in study analysis and reporting.

Visit 4 (Post-operative Assessment): Post-operative evaluation. The patients return to clinic at 1 month (+/- 2 weeks) after completion of visit 3 for a wound evaluation, device check, and symptom review. At this point, the patients will complete study questionnaires (on paper, over the phone/teleconference system, or electronically through REDCap) and undergo a repeat ARM.

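### Section 6.3 compares total leakage counts with no time unit or fixed baseline length: 28 baseline days against a 14-day test shows a 50% decrease with no change in leakage

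*Combined protocol and SAP*

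**What the plan says.** Section 6.3 defines SNS Success as having the battery implanted at Visit 3, which requires improvement in fecal incontinence. Incontinence is the "total number of gas, mucus, liquid stool, and solid stool accidental leakage events reported in the bowel diaries". The physician judges improvement from "bowel diary comparisons recorded before SNS lead placement at visit 1 to after lead placement at visit 2".

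The threshold is in Section 5, Visit 3: if the diary shows at least a 50% "decrease in FI or LARS symptoms between visit 1 and visit 2, the external temporary battery will be replaced with an implantable battery". Below 50%, lead position is checked and properly placed leads are removed.

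The diary periods are described only in Section 5:

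- **Baseline start** (Initial Evaluation/Visit 1): "All patients are asked to begin recording all daily bowel and bladder habits in the bowel and bladder" trackers. No end date or number of days is given.
- **Lead placement** (Visit 2): "Surgery for stage 1 sacral nerve stimulator placement will occur within 30 days after enrollment in the study". Table 1 shows Visit 2 at + 4 weeks.
- **Test diary** (Study Procedures): "A bowel and bladder habit diary is maintained by the patients for the interval 2 week period".
- **Visit 3**: "will occur around 2 weeks (+7 days) after SNS placement".
- **Migrated lead** (Study Procedures): "lead repositioning will be performed and the two week trial period restarted".

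Table 1 marks the diary at Visits 1 and 2 without a length. Weekly episode rates appear in Section 2, but only as results of other studies.

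**The concern.** A total count grows with the number of days recorded. Comparing two totals is fair only if the two diaries cover the same number of days, and nothing in the text makes them do so. Baseline has a start and no stop. The natural reading, which is an inference, is that it runs until lead placement, so its length is set by surgical scheduling. The test diary has a nominal 14 days. Unequal periods can therefore arise without any protocol deviation.

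The error can go either way. A baseline longer than the test makes the 50% rule easier to meet, and a patient without benefit may receive a permanent implant. A shorter baseline makes it harder, and a true responder may have the leads removed, which ends participation. Each such decision is also a primary endpoint result, and Section 6.6 reads a success rate of 50% or better as confirming efficacy in the surgery cohort and as warranting further study in the radiation cohort.

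**Working it through.** **The plan's own figures.** The documents give no figure for diary length. The nearest stated figure for this endpoint is the 90% credible interval for 15/30 in Section 6.4. The 5th and 95th percentiles of Beta(16, 16) are 35.7% and 64.3%, as stated. The futility bounds 0/3/5/7/10 in Section 6.5 also reproduce.

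**Inputs.** L = baseline days, anything up to 30 (Section 5, Visit 2). T = test days, 14 (Study Procedures), possibly up to 21 (Visit 3 window). w = leakage episodes per week: 7.5 (Section 2, studies that excluded rectal cancer), with 49 as an alternative (7 per day × 7, from the Section 2 review of patients treated for rectal cancer). r = true proportional reduction.

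**Step 1: exact arithmetic, raw totals.**

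- Apparent decrease with no change = 1 − T/L
- True reduction needed to pass = 1 − 0.5 × L/T

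| L (T = 14) | Apparent decrease, no change | True reduction needed |
|---|---|---|
| 7 | total doubles | 75% |
| 14 | 0% | 50% |
| 21 | 33% | 25% |
| 28 | 50% | 0% |

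With T = 21 and L = 28 the apparent decrease is 1 − 21/28 = 25%.

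**Step 2: one patient, with chance variation.** Assume independent counts B ~ Poisson(Lw/7) at baseline and X ~ Poisson(T(1 − r)w/7) on test. Totals pass if X ≤ B/2; rates pass if X/T ≤ 0.5 × B/L; both need B > 0.

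No benefit (r = 0), T = 14:

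| L | Totals, w = 7.5 | Rates, w = 7.5 | Totals, w = 49 |
|---|---|---|---|
| 14 | 4% | 4% | 0% |
| 21 | 22% | 3% | 1.7% |
| 28 | 53% | 3% | 51% |
| 30 | 61% | 3% | 72% |

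- Lower and higher rates, L = 28: at w = 3.5 and 14, totals give 54% and 52%, rates 11% and 0.4%.
- Longer test, T = 21, L = 28, w = 7.5: totals give 9%.
- Responder, r = 0.6, L = 7, T = 14, w = 7.5: totals pass 24% of the time, rates 71%.

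**Step 3: one cohort of 30.** Average the pass probability over baselines spread evenly across a range of days, then compute by exact binomial, in groups of 6, the chance of at least 15/30 without stopping at 0/6, 3/12, 5/18 or 7/24. Adverse-event stops are ignored. T = 14, w = 7.5, totals:

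| Baseline days | Mean pass, r = 0 | P(≥15/30), r = 0 | P(≥15/30), r = 0.3 |
|---|---|---|---|
| 7–30 | 0.208 | 0.0003 | 0.42 |
| 14–30 | 0.288 | 0.011 | 0.93 |
| 21–30 | 0.416 | 0.22 | – |
| all 28 | 0.528 | 0.68 | – |

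On rates, the r = 0.3 figures are 0.0006 (7–30 days) and 0.0004 (14–30 days). At w = 49 on totals, the r = 0.3 figures are 0.37 and 0.96, against essentially 0 on rates. The no-benefit figures at w = 49 fall to 0.00005 (14–30 days) and 0.016 (21–30 days).

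With T = 21 and w = 7.5, the four no-benefit means on totals are 0.027, 0.038, 0.061 and 0.090, and every cohort probability is below 0.00001. For r = 0.3 the means over 7–30 and 14–30 days are 0.176 and 0.245, giving 0.00005 and 0.002.

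**The case against.** The strongest reply is that the recording length may sit on a form not available here. The diary is the device company's tracker (Appendix I), listed but not shown. If it fixes a 14-day baseline and the test is 14 days, there is no distortion. That stands as a limit on the conclusion.

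Second, the 28-against-14 case needs several conditions together: baseline running to placement, surgery late in the window, a test of exactly 14 days, and no adjustment by the physician. This also stands as a limit. Averaged evenly over baselines of 7–30 days and tests of 14–21 days, the no-benefit pass rate on totals is about 10% at 7.5 episodes a week, not 53%. A strong responder is little affected: with a 90% reduction, about what Section 2 reports (7.5 to 0.67), totals pass at least 99.7% of the time at baselines of 14–30 days, and 91% at 7 days.

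Third, the physician judges improvement, reviews symptoms with the patient, and can see that one diary covers more days. Section 5 also speaks of FI or LARS symptoms rather than a raw total. But Section 6.3 names the total as the measure and nothing instructs a conversion. Informal adjustment in an open single-arm study could differ from patient to patient.

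Fourth, 7.5 episodes a week comes from studies that excluded rectal cancer. At 49 a week the no-benefit distortion nearly vanishes at 21 days but remains at 28–30, and the cohort result for a 30% reduction hardly changes.

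**Conclusion.** The concern holds as a conditional one. That the visible text supplies no denominator, baseline length or matched periods is certain. Where the two diaries differ in length and totals are compared, the true reduction needed to pass moves from 75% at 7 baseline days to 0% at 28, for a 14-day test.

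For a treatment with no effect at all, a false positive cohort is unlikely unless baselines cluster late. The greater exposure is a modest effect: a true 30% reduction in every patient, which the plan's own rule should reject, reaches 15/30 with probability 0.42 to 0.93 on totals against less than 0.001 on rates. Those figures assume a 14-day test, baselines spread evenly over 7–30 or 14–30 days, and Poisson counts at 7.5 a week without day-to-day clustering. A 21-day test largely removes the upward bias for those spreads, and makes passing harder for patients with shorter baselines.

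The plan should be changed because the primary endpoint and an implant decision rest on this comparison. Confidence in the realised size is medium: the actual mix of baseline lengths, the tracker form and clinic practice are not in the documents.

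**What to change.** In Section 6.3, replace the total with leakage events (gas, mucus, liquid and solid summed) per recorded diary day. In Section 5, Visit 3, apply the 50% rule to the two daily rates. Preferably use up to the last 14 recorded days before lead placement and the first 14 recorded days after it, or after repositioning if the two-week trial restarts. The sponsor should set a minimum number of recorded days for each period. If the Appendix I tracker already fixes these lengths, Section 6.3 should state them.

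The cost is wording in two places and one division per patient. The diary is already daily, so no new form, visit or surgery date is needed. Short baselines give a noisier rate: at 7.5 episodes a week and a 14-day test, a no-benefit patient passes 7% of the time with 7 baseline days, against 4% with 14. This is the reason for a minimum.
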